18.3 Definition of device deficiency

Device deficiency (DD)* is defined as inadequacy of a device with respect to its identity, quality, durability, reliability, safety, or performance, including malfunctions, use errors and inadequate labeling.

*see ISO 14155 3.15

DDs of the investigational device shall be documented throughout the study. DDs which caused an adverse event are reported on the respective adverse event form. In case the DD did not cause an adverse event the provided DD form shall be used to document this "non-medical" event.

If a DD could have led to a SADE,

- if either suitable action had not been taken,
- if intervention had not been made, or
- if circumstances had been less fortunate,

the DD is classified as an DD with an SADE potential.

18.4 Definition of serious adverse events

AEs are classified as serious* if one or more of the following consequences are fulfilled:

- led to death
- led to serious deterioration in the health of the subject, that either resulted in
- a life-threatening illness or injury, or
- a permanent impairment of a body structure or a body function, or
- in-patient or prolonged hospitalization, or
- medical or surgical intervention to prevent life-threatening illness or injury or permanent impairment to a body structure or a body function.
- led to fetal distress, fetal death or a congenital abnormality or birth defect.

Note: Planned hospitalization for a pre-existing condition, or a procedure required by the CIP, without serious deterioration in health, is not considered a serious adverse event.

*see ISO 14155 3.37

In-patient hospitalization is defined as at least one overnight stay (change of date) in a hospital. In case, a patient is only for some hours in the hospital (without change of date), this event will not be documented as serious, unless one or more of the other seriousness criteria are fulfilled.

18.4.1 Patient death

If the death of a patient emerges during the study this SAE might be subject to special reporting requirements in some countries. Therefore as much information as possible should be provided to enable BIOTRONIK to explain the circumstances leading to the death. At least a pseudonymized copy of the death records documenting the cause of death, an autopsy report (if performed) and a doctor's letter detailing the medical history and the circumstances of the death should be sent to BIOTRONIK promptly.

On the AE-CRF, the following information should be provided, if available:

- Cause of death
- Date and time of death
- Place death occurred
- Statement whether the event was device or study procedure related

In addition to the adverse event eCRF a study termination form has to be completed.

Whenever possible, devices that are explanted must be returned to BIOTRONIK SE & Co. KG for analysis.

18.5 Definition of serious adverse device effect

An ADE* that resulted in any of the consequences characteristic of a serious adverse event is considered serious.

*see ISO 14155 3.36

18.6 Definition of unanticipated serious adverse device effects

SADs* are defined as unanticipated if by their nature, incidence, severity or outcome they have not been identified in the current version of the risk analysis report.

*see ISO 14155 3.42

These events must be reported to the sponsor immediately.

A root-cause analysis will be performed and the possibility of reoccurrence will be evaluated immediately.

Note: Anticipated serious adverse device effect (ASADE) is an effect which by its nature, incidence, severity or outcome has been identified in the risk analysis report.

18.7 Anticipated adverse events

The following peri- or post-operative risks are anticipated with the insertion of the BIOMONITOR III and are therefore assessed as procedure related adverse device effects. They are listed in **Table 3** as sorted by their incidence rates. For all references used for this chapter, refer to the list at the end of this section.

Table 3: Anticipated AEs based on literature research sorted by incidence rate

Frequency	Event Type	Reference ID
Frequent 1 to 10 patients out of 100	Insertion site irritation/soreness	4, 9
	Insertion site erosion	3, 9
	Insertion site pain	1, 2, 3, 5, 8, 11
	Insertion site dehiscence/device protrusion/extrusion	2, 7, 13, 15
	Insertion site infection	1, 2, 3, 5, 6, 7, 8, 9, 10, 11, 12, 15
	Insertion site hematoma	3, 7, 14
Occasionally 1 to 10 patients out of 1.000	Insertion site hemorrhage	1, 8, 13
	Insertion site discomfort	5, 12
	Insertion site bruising	2, 13
	Incision site complication	8, 13
	Device dislodgement/migration	3, 5, 13, 14
Not known Frequency not assessable on the basis of the available data	Oversensing, Undersensing, Premature battery depletion, Electromagnetic interference (EMI), Impaired healing, Insertion site rash, Non-insertion site rash, Non-insertion site pain, Numbness of upper arm, Procedural dizziness, Post procedural dizziness, Post procedural nausea, post procedural headache, Dyspnea, Vagal reaction, Presyncope, Supraventricular tachycardia, Shock/dyspnea (reaction to antibiotic administration prior to device insertion), Device interrogation issue, Home Monitoring transmission incomplete/missing, Housing surface conspicuous before implantation, Varying P/R values, Device in safety back-up mode, Silicone coating damaged, Foreign body rejection phenomena, Accumulation of fluid in the device pocket	1, 2, 3, 5, 6, 13, 16, 17

1. BIOTRONIK. CIR Master Study of the Implantable Cardiac Monitor BioMonitor 2015.
2. BIOTRONIK. CIR BioMonitor 2 Pilot Study 2016.
3. BIOTRONIK. CIR BIO|MASTER.BioMonitor 2 2017.
4. Bisignani G, Bonis S de, Bisignani A, Mancuso L, Giacomelli D. Sensing performance, safety, and patient acceptability of long-dipole cardiac monitor: An innovative axillary insertion. *Pacing Clin Electrophysiol* 2018;**41**:277–283.

FOR-137-014-F / SOP-137-020.020 / CRQ170002722

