18.1 Definition of adverse events

An AE is defined* as any untoward medical occurrence, unintended disease or injury, or untoward clinical signs (including abnormal laboratory findings) in subjects, users or other persons whether or not related to the investigational device. This includes:

- Events related to the investigational device or the comparator
- Events related to the procedures involved
- For users or other persons, this definition is restricted to events related to the investigational devices.

*see ISO 14155 3.2

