18.2.1 Causality Assessment

The relationship between the use of the investigational device (including the medical-surgical procedure) and the occurrence of each adverse event shall be assessed and categorized, considering the presence of confounding factors, such as concomitant medication and treatment, the natural history of the underlying disease, other concurrent illness or risk factors.

Each AE will be classified according to five different levels of causality. As defined in the Meddev 2.7/3 rev 3, the investigator will use the following definitions to assess the relationship of the adverse event to the investigational device or procedures and the sponsor will review the investigators categorization:

Not related: the relationship to the device or procedures can be excluded

Unlikely: the relationship with the use of the device seems not relevant and/or the event can be reasonably explained by another cause, but additional information may be obtained.

Possible: the relationship with the use of the investigational device is weak but cannot be ruled out completely. Alternative causes are also possible (e.g. an underlying or concurrent illness/ clinical condition or/and an effect of another device, drug or treatment). Cases where relatedness cannot be assessed or no information has been obtained should also be classified as possible.

Probable: the relationship with the use of the investigational device seems relevant and/or the event cannot reasonably explained by another cause, but additional information may be obtained.

Causal relationship: Causal relationship: the serious event is associated with the investigational device or with procedures beyond reasonable doubt.

The investigators will distinguish between the adverse events related to the investigational device and those related to the device procedures (any procedure specific to the investigational device). Procedure related events refers to the procedure related to the application of the investigational device only and therefore not to any other procedure for other devices and not to any other procedures or treatments applied later throughout the clinical investigation, for instance to treat (serious) adverse events. In case of a replacement of the investigational device in response to an adverse event (e.g. replacement after device migration), the replacement will be considered like an initial application of a new investigational device and shall be assessed accordingly.

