18.9 Reporting timelines

The reporting timelines for the investigator are displayed in **Table 4**.

Table 4 Reporting timelines

Event	Report to	Timeline
Adverse Event (AE) / Adverse Device Effect (ADE)	CCR BIOTRONIK SE & Co. KG: Documentation in the AE CRF	Preferably within 2 weeks
Serious Adverse Event (SAE) / Serious Adverse Device Effect (SADE)	CCR BIOTRONIK SE & Co. KG: Documentation in AE-CRF	Immediately, latest 24h after detection
Unanticipated Serious Adverse Device Effect (USADE)	CCR BIOTRONIK SE & Co. KG: Documentation in AE-CRF	Immediately, latest 24h after detection
Device Deficiencies	CCR BIOTRONIK SE & Co. KG: Documentation in the DD-CRF	Preferably within 14 days
Device Deficiency with SADE potential	CCR BIOTRONIK SE & Co. KG: Documentation in DD-CRF	Within 24 hours

The obligation to assess and report SA(D)Es and Serious Device Deficiencies to the sponsor without unjustified delay is an important part of the Principal Investigator's responsibilities as defined by ISO 14155:2011. This obligation is not restricted to scheduled patient follow ups according to the CIP, but it is a continuous responsibility for the duration of the study, making sure that any unexpected risks originating from the study procedures or the investigational product are identified as soon as possible and patients are adequately protected. The Principal Investigator is responsible to set up appropriate workflows at his/her site, making sure that:

- the site study team is continuously informed on any relevant interactions or interventions concerning study patients at the site, regardless if members of the study team are directly involved or not;
- if the site is part of a larger organizational structure - e.g. a multi-faculty-hospital - a notification system is in place, making sure that other departments / clinics are aware of the patient's study participation and that relevant events, such as hospitalizations, are notified to the site study team without delay;
- if information on relevant events from external sources reaches the site (e.g. medical reports from other facilities), these are made available to the study team without delay.

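### Section 18.7 attributes every Table 3 item, technical faults included, to the procedure as an adverse device effect, which contradicts 18.1 to 18.3 and could misroute or miscount events

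*Protocol*

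**What the plan says.** Section 18.7 introduces Table 3 by saying that the peri- and post-operative risks are "anticipated with the insertion of the BIOMONITOR III and are therefore assessed as procedure related adverse device effects". It then adds "They are listed in Table 3 as sorted by their incidence rates", so the attribution reaches the whole table. Section 6.2.1 refers readers to 18.7 for the anticipated adverse device effects.

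Most of Table 3 is wound and procedural events. The last row, for events of unknown frequency, also contains "Device interrogation issue, Home Monitoring transmission incomplete/missing, Housing surface conspicuous before implantation, Varying P/R values, Device in safety back-up mode, Silicone coating damaged", together with oversensing, undersensing, premature battery depletion and electromagnetic interference.

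Other parts of section 18 set the classification rules:
- 18.1 defines an AE as "any untoward medical occurrence, unintended disease or injury, or untoward clinical signs", and 18.2 defines an ADE as an AE related to use of the device.
- 18.2.1 has each AE graded on five causality levels and adds: "The investigators will distinguish between the adverse events related to the investigational device and those related to the device procedures".
- 18.3 deals with deficiencies that harmed nobody: "In case the DD did not cause an adverse event the provided DD form shall be used".
- Table 4 in 18.9 has a row for "Device Deficiency with SADE potential", due within 24 hours on the deficiency form. A non-serious AE or ADE is due preferably within two weeks on the AE form.

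**The concern.** The sentence in 18.7 decides three things in advance that the rest of section 18 leaves to the individual event: that it is an AE, that it is device-related, and that the procedure is responsible. For a technical fault without clinical consequence, all three conflict with the definitions.

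The classification feeds the results. The synopsis lists ADEs, procedure- or device-related, as data of interest. Section 7.2.2 lists AEs and deficiencies associated with the insertion procedure and tools, and 5.3 makes insertion success and safety the main focus. Up to 15 sites classify events, and the interim analysis in 11.6 is to support the launch decision. With 45 patients, one patient wrongly counted as having a procedure-related ADE moves a patient-level rate by 1/45 = 2.2 percentage points. The reporting route also differs: 18.3 defines SADE potential for deficiencies only.

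**Working it through.** The protocol states no figure to reproduce here. The check compares texts and adds a count of the table.

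**Scope of the sentence.** The second sentence of 18.7 refers the risks as a group to Table 3. No row is excepted.

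**Count of Table 3 items.** 6 frequent + 5 occasional + 26 of unknown frequency = 37. I class 10 as technical: oversensing, undersensing, early battery depletion, electromagnetic interference, interrogation issue, missing transmission, conspicuous housing, varying P/R values, safety back-up mode and damaged coating. That is 10/37 = 27%. The protocol does not make this classification. Oversensing, undersensing, interference and varying P/R values are borderline, and without them it is 6/37 = 16%. All are in the row of unknown frequency.

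**One fault under each section.** Take a missed Home Monitoring transmission with no effect on the patient.

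| Question | 18.7 read literally | 18.1 to 18.3 and 18.9 |
|---|---|---|
| Is it an AE? | Yes, since it is called an ADE | No: no medical occurrence |
| Related to the procedure? | Yes, in advance | Not asked; would be graded per event if an AE existed |
| Form | Not stated; an ADE would go on the AE form under Table 4 | Deficiency form |
| SADE potential asked? | Not for an ADE | Yes |
| Timeline | Preferably two weeks if non-serious | 24 hours with SADE potential, otherwise preferably 14 days |

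The housing flaw is the clearest case. It is found before implantation, so it cannot by itself be a medical event in the patient caused by the insertion.

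**Medical rows.** The conflict with 18.2.1 reaches these too. Table 3 lists presyncope and supraventricular tachycardia, while section 8.3.2 admits patients under investigation for pre-syncope or a suspected arrhythmia. Section 18.2.1 requires the natural course of the underlying disease to be weighed; 18.7 would settle the attribution without that step.

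**The case against.** The strongest reply is that 18.7 is background. Its table is captioned as a literature-based list, and the section prescribes no form, timeline or counting rule. Section 18 opens by tying classification to its definitions, and 8.1.4.7 repeats that events are classified by seriousness and by relation to device and procedure. Under 18.2.1 the sponsor reviews the investigator's causality category. Section 18.8.1 requires a deficiency form for device deficiencies, and 18.9 keeps the 24-hour row. Whether a SADE counts as anticipated depends on the risk analysis report (18.6), not on Table 3. There are no endpoints, hypotheses or pass/fail criteria. Section 7.2.2 lists AEs and deficiencies associated with insertion as one item, so a misfiled insertion-related fault would still appear there.

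Most of this stands. A reader might infer that ADE counts are inflated, or that technical faults escape the 24-hour route. The documents do not support either as fact: 18.1 to 18.3 and 18.8.1 remain in force, and nothing says that 18.7 overrides them.

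What does not stand is that the sentence is only a list. It says how the items are assessed, and 6.2.1 sends readers there for the anticipated device effects. A site that follows it is following the protocol, and so is a site that follows 18.3.

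**Conclusion.** The contradiction is real and can be read directly from the text. Section 18.7 cannot be reconciled with 18.1, 18.2, 18.2.1 and 18.3 for the technical items. The consequence is a possibility: technical faults could be counted as procedure-related ADEs, or handled on the slower AE route without the SADE-potential question, at sites that read 18.7 literally.

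The size of any effect cannot be estimated from the protocol. It is tempting to use the transmission success claim in 7.3 (TSI above 90%). At 90% daily success over 30 independent days, the share of patients with at least one missed message is 1 − 0.90^30 = 95.8%; at 95% it is 78.5% and at 99% it is 26.0%. These are not estimates of ADE inflation. The protocol does not define TSI as a daily probability per patient, independence of days is assumed, and every missed message would have to be filed as an AE, which no section instructs. Under 18.3 this item adds nothing to the ADE count.

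The conclusion does not depend on how the borderline items are classed. It is a wording defect worth correcting, because the sentence would misclassify events if followed.

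**What to change.** - Delete the blanket attribution in 18.7, or limit it to calling the listed events anticipated.
- Split Table 3 into medical events and technical events.
- State that relation to device and to procedure is judged per event under 18.2.1.
- State that a technical fault without an AE goes on the deficiency form, with the SADE-potential question answered there.
- State that an AE caused by a technical fault goes on the AE form and counts as an ADE under 18.2. Without this line, an ADE rate taken only from the medical list could lose AEs that result from malfunction, which 18.2 expressly includes.

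The cost is a short amendment. Section 13 treats changes that affect study procedures or data analysis as substantial, so ethics approval may be needed before it takes effect. No new data, visits or patients are required.

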18.8 Reporting responsibilities

18.8.1 Reporting responsibilities of the investigator to sponsor

The investigator shall document all events on the respective CRF pages provided within the CDMS. The indicated timelines for reporting of initial cases and possible update reports shall be strictly followed.

All Serious Adverse Events (SAE) and Serious Adverse Device Effects (SADEs) shall be reported together with an assessment by completing the AE-CRF in accordance with ISO 14155:2011.

For device deficiencies of the investigational device, a DD-CRF shall be completed.

The reports shall be done with all information available, even if this results in an incomplete report. The investigator has to follow-up ongoing (S)A(D)Es either as long as the patient participates in the study, the clinical investigation is terminated prematurely or until the event has been resolved, whatever comes first. SADEs ongoing SADEs at the subjects regular study termination should be followed up for further four weeks or until resolution whatever comes first. Ongoing SADEs related to the investigational device will be followed until termination of the study if not resolved before.

Multiple events may occur simultaneously in one subject. For each medically independent event an individual report must be provided.

In addition, the action taken/ treatment should also be provided with any supportive documentation available.

The investigator has to ensure that all relevant information is available. This also includes information from other parties (family, other hospitals etc.).

If a patient dies during the study this might be subject to special reporting requirements in some countries. Therefore as much information as possible should be provided to enable BIOTRONIK to explain the circumstances leading to the death. At least a pseudomized copy of the death records and an autopsy report (if performed) should be sent to BIOTRONIK promptly. All actions taken, which were initiated to gain further information must be documented in writing and provided to BIOTRONIK.

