9.8 Termination and post treatment

The study termination eCRF must be completed to determine the end and reason for study termination of the individual patient. The regular termination of the patient is defined as the time when the 1-month Home Monitoring observation and telephone interview is completed. The frequency and elements of routine visits according to standard guidelines for ICM therapy are adequate for all patients after regular study termination.

In the case of patients who do not show up for the scheduled 1-week follow-up, all efforts should be made to contact them and complete the required checks, even if this would be far out of the planned schedule. Equally, all efforts should be made to contact the patient for the 1-month follow-up to assure that no adverse events will remain unnoticed. It should be kept in mind that the study device has no market approval and is implanted only under the condition that the patient is followed in this study.

Follow-up of subjects which have withdrawn consent is covered in section 8.3.5.1.

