20 SUSPENSION

20.1 Criteria and procedures

Suspension or premature study termination at an investigational site may occur due to several reasons:

- On behalf of the sponsor
- On behalf of the investigator
- On behalf of the EC

The sponsor is authorized to terminate the clinical study prematurely due to relevant medical/organizational reasons.

A consultation of all parties involved prior to study termination is preferable. Reasons for premature study termination should be documented in an adequate way.

The sponsor has the right for premature study termination of the whole study, of single study phases or arms, or to exclude single investigational sites from further study participation.

Reasons for termination may be:

- Occurrence of severe Adverse Events that result in a non-acceptable risk for further study participation.
- The number of premature study terminations exceeds the tolerable percentage of drop-outs so that proper completion of the study cannot be expected anymore.
- Insufficient enrollment rates so that proper completion of the study cannot be expected anymore.
- Results from other clinical investigation indicate a non-tolerable risk for further conduction of this study.
- Attempted fraud or fraud that may be evidenced.
- Poor data quality
- Missing compliance of the respective investigator or study site (e.g. protocol violations).

In case the study sponsor decides to suspend or prematurely terminate the study, the sponsor is required to promptly notify the investigator(s) to whom the decision applies. The investigator will inform the EC of this decision. The investigator will also promptly inform all patients enrolled at the investigational site and are still actively participating. Patients that already left the study shall be informed if they might be affected by safety aspects.

In case of any reasonable ethical concern of the investigator regarding a further study conduct in the respective investigational site, the sponsor shall be informed immediately.

If the investigator decides to suspend or prematurely terminate the study at his/her site he/she will promptly inform the study sponsor, the EC and all enrolled patients of this decision.

If the EC decides to suspend or prematurely terminate the study, the investigator will promptly inform the study sponsor (or vice versa as applicable) and all enrolled patients of this decision.

The eCRF for `Study Termination` has to be completed in all of the above cases.

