20.2 Requirements for subject follow-up

In case of a study suspension no new patients will be enrolled until the suspension has been lifted. During the suspension, follow-up and data collection will continue as per CIP. If the suspension is due to an EC decision, additional requirements from the EC with respect to follow-up and data collection may apply.

If an (S)A(D)E is ongoing at time of the last study related visit or study termination, whatever comes first, the outcome of the event has to be updated to 'Ongoing at study termination'. SADEs ongoing at the subjects regular study termination should be followed up for further four weeks or until resolution whatever comes first.

Patients have to be informed on this procedure in written form in the patient informed consent form.

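### The four further weeks of follow-up for an ongoing serious adverse device effect apply only after regular termination, so none is required after an early stop

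*Protocol*

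**What the plan says.** Three sentences in Protocol 18.8.1 set how long an ongoing event is followed.

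1. Ongoing (S)A(D)Es are followed until the patient leaves the study, "the clinical investigation is terminated prematurely or until the event has been resolved, whatever comes first".
2. SADEs ongoing "at the subjects regular study termination should be followed up for further four weeks or until resolution whatever comes first".
3. "Ongoing SADEs related to the investigational device will be followed until termination of the study if not resolved before".

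Section 9.8 fixes the key term: "The regular termination of the patient is defined as the time when the 1-month Home Monitoring observation and telephone interview is completed".

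Section 20.1 lists reasons for premature termination. The first is "Occurrence of severe Adverse Events that result in a non-acceptable risk for further study participation". Section 20.2, on subject follow-up, covers a suspension: "During the suspension, follow-up and data collection will continue as per CIP". For an event still open at the last visit or at study termination, it has the outcome recorded as ongoing. It then repeats the four weeks, again for regular termination only.

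Section 5.3 says that possibly related SAEs get four additional weeks and does not restrict this to regular termination. Section 8.3.4.2 keeps patients with a failed insertion or an explantation in the study until all their adverse events have ended.

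**The concern.** The extension depends on how the patient's participation ends. A patient who completes month 1 with an unresolved SADE is followed for up to four more weeks. A patient with the same event who is cut off before month 1 because the study was stopped is not. One listed reason for stopping is unacceptable harm, so the plan requires the shorter follow-up in the setting where the outcome of a serious device effect is most informative.

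The device had not been inserted in a living person before this study (4.8), and safety of the insertion procedure is a stated objective (7.1). Section 9.8 adds that the device "is implanted only under the condition that the patient is followed in this study". At stake is the recorded outcome of a small number of serious events in a first-in-human report.

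**Working it through.** The plan gives no figure to reproduce, so this is mainly a comparison of rules.

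**What is required for an unresolved SADE**

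| How participation ends | Governing text | Required follow-up after that date |
|---|---|---|
| Regular termination | 18.8.1 sentence 2; 20.2 | up to 4 weeks |
| Failed insertion or explantation | 8.3.4.2 | until the events have ended |
| Suspension | 20.2 | continues as planned |
| Study stopped before month 1, device in place | 18.8.1 sentences 1 and 3; 20.2 | none |

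In the last row, sentence 1 names premature termination as a stop point. Sentence 2 does not apply, because the patient has not reached regular termination. Sentence 3 ends when the study ends. Section 20.2 adds nothing except the outcome entry.

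If only one site is closed, sentence 1 ends follow-up with the patient's participation. Sentence 3 can then be read as carrying an SADE related to the device itself on to the end of the study. Other SADEs, such as those related only to the procedure, have no such cover.

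**Days lost per event**

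Take month 1 as day 30 (9.5 uses the recording closest to 30 days) and let the stop fall d days after insertion, with d from 0 to 30.

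- Required now: to day d.
- Required if the four weeks also applied to a premature stop: to day d + 28 at the latest.
- Loss due to the wording: (d + 28) − d = 28 days at most, and fewer if the event resolves sooner.

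**Patients in the exposed window**

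This assumes 45 insertions spread evenly over the enrolment period, which 8.3.6 puts at about 3 months. At mid-enrolment, the number implanted and before month 1 is:

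- over 90 days: 45/90 × 30 = 15
- over 120 days: 45/120 × 30 = 11.25, about 11
- over 60 days: 45/60 × 30 = 22.5, about 23

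These are patients in the window, not patients with an SADE. For scale only, 5.2.2 reports two patients with an SADE in the predecessor's master study, with 90 successful insertions and events counted to the 3-month follow-up. At that rate, 15 patients would have 15 × 2/90 = 0.33 expected. The device differs and the counting period was longer than one month. A safety stop would also imply a higher rate. The figure shows that the affected group is small; it is not a forecast.

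**The case against.** **Section 5.3 shows the safer intent.** It promises four more weeks without the word *regular*. This stands as evidence of intent. It does not settle the matter, because 5.3 is a justification statement and uses a different event class (possibly related SAEs), while 18.8.1 and 20.2 are the operative rules. The document contradicts itself and should be aligned.

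**An immediate cut-off is not the only route.** The sponsor may suspend or end single phases under 20.1, and follow-up continues during a suspension. Section 8.3.6 also defines study end by the last patient's termination. This narrows the case, but premature termination of the whole study is provided for, and sentence 1 makes it a stop point.

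**Outcomes could still become known.** A reader might infer that the report could not say how such events ended. The documents do not support that. Section 20.1 has open eCRFs completed as far as possible, and 18.8.3 has SADEs reported to authorities as local rules require. Section 18.6 demands a root-cause analysis of unanticipated SADEs, and nothing forbids collecting later information. Both predecessor SADEs ended in explantation, which 8.3.4.2 would cover here. What is missing is a required follow-up period, not every means of learning the outcome.

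**The loss could be put higher.** Regular follow-up could run to day 30 + 28 = 58, so a reader might infer a loss of 58 − d, or 28 to 58 days. But 58 − d = 28 + (30 − d), and the second term is ordinary participation ended by the stop itself. The wording does not cause that loss, and extending the four weeks would not restore it.

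**Withdrawal.** Section 9.8 states: "Follow-up of subjects which have withdrawn consent is covered in section 8.3.5.1". No such section exists. A reader might infer a second safety gap for patients who withdraw with the device in place. The likely target is 8.3.4.3, where ending data collection respects the patient's decision. Care after withdrawal may be described in the consent form, which is not at hand. What remains is a wrong section number.

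**Conclusion.** The point holds in a narrow form. After a premature stop of the study, an unresolved SADE in a patient before month 1 who still has the device has no required follow-up. The same event after regular termination would have up to four weeks. For a site closure this holds at least for SADEs not related to the device itself. The rule also contradicts 5.3.

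The cost is at most 28 days of follow-up per unresolved SADE. About 15 implanted patients (11 to 23) would be in the window at mid-enrolment if insertions are evenly spread. Few of them would have an unresolved SADE. The documents give no event timing, so no probability is stated. If the study runs to plan, nothing changes, and no planned analysis is affected. The change is still worth making, because the stated rule is weakest after a stop for harm and the correction is small.

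**What to change.** In 18.8.1, replace the second sentence and repeat the rule in 20.2, for example: *An SADE ongoing at the subject's regular termination, or at premature termination of the study or site, is followed for four further weeks from that date or until it resolves, whichever is sooner.* Amend the first sentence so that premature termination is no longer an earlier stop point for SADEs. State that the third sentence, on device-related SADEs, does not shorten these four weeks. In 5.3, use the same event class (SADE) and the same rule.

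Editorial only: in 9.8, change the reference from 8.3.5.1 to 8.3.4.3.

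Cost: section 13 makes a change to study procedures a substantial amendment, which needs ethics approval. Section 20.2 already requires the consent form to describe this follow-up, so that wording must match. No visit or data item is added if the study runs to plan. After an early stop, the adverse event forms of affected patients stay open for up to four more weeks.
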